### 9.1.3 Rescue period

Subjects with a reduction in the CDAI of less than 70 compared to baseline after finishing evaluation in Week 12 of the remission-induction period are to move on to the rescue period. The rescue period is to last 12 weeks, with 10 mg/kg of E6011 administered in an unblinded manner on Week 12, Week 13, Week 14 and every two subsequent weeks until Week 22.

The Principal Investigator or Sub-investigator is to confirm before the first evaluation in the rescue period is carried out that non-responders' data up to Week 12 of the remission-induction period (double-blind period) has been entered in the case report form. Blinding of each subject's treatment group is to be maintained until the database of the remission-induction period is locked.

Subjects with a reduction in the CDAI of 70 or more compared to baseline or Week 12 at evaluation in Week 24 are to move on to the extension period. Subjects with less than 70 reduction in the CDAI compared to baseline and Week 12 are to be discontinued.

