#### 9.3.1 Inclusion criteria

Subjects who meet all the following criteria are eligible to participate in this clinical trial.

- (1) Crohn's disease patients aged 18 or over and under 65 on the date of consent.
- (2) Patients diagnosed on basis of clinical findings, endoscopic findings, etc. with small intestine-type, small and large-intestine type, or large-intestine type Crohn's disease at least 12 weeks before giving consent.
- (3) Patients with a baseline (at Week 0 before the start of IMP administration) disease severity ranging from moderate to severe. CDAI score between 220 and 450, and a PRO2 score between 14 and 34.
- (4) Patients with a Simple Endoscopic Score for Crohn's Disease (SES-CD) ≥7 (or for patients with isolated ileal disease, ≥4 in ileum segment) in the screening period, with one or more ulcers (in SES-CD score, ulcer presence subscore ≥ 1 in any segment) assessed by colonoscopy and confirmed by a centralised review.
- (5) Patients who received adrenocorticosteroids or immunomodulators in the past, but showed no therapeutic response (insufficient response) or the drugs were not tolerated (intolerance). Alternatively, patients who cannot taper adrenocorticosteroids (dependence). Alternatively, patients who showed no therapeutic response after administering biologic(s) (primary nonresponse), patients who initially showed therapeutic response but it lessened or disappeared afterwards (secondary nonresponse), or patients who did not tolerate the drug (intolerance). (Detailed criteria are described in Attachment 7 and Attachment 8).
- (6) If the patients are taking 1,200 kcal/day or less enteral nutrition, the dosage and administration have not changed for at least 4 weeks prior to the start of the IMP administration.
- (7) If the patients are taking aminosalicylic acid (5-ASA), salazosulfapyridine, or antibiotics for the treatment of Crohn's disease (metronidazole, ciprofloxacin, etc.), the dosage and administration have not changed for at least 4 weeks prior to the start of the IMP administration.
- (8) If the patients are taking under 30 mg/day of oral prednisolone (or equivalent adrenocorticosteroid) or 9 mg/day or less of oral budesonide, the dosage and administration have not changed for at least 4 weeks prior to the start of the IMP administration.

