In the evaluation of disease activity level based on CDAI scores, CR70 and CR100 are defined as clinical response with a decrease of  $\geq$  70 points and  $\geq$  100 points from baseline, respectively, and remission is defined as CDAI < 150.

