# 9.7.1.10 Analysis of the entire dosing period

The same efficacy, pharmacokinetic, biomarker, immunogenicity, and safety analyses performed for the remission-induction period are to be performed.

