4 ANALYSIS ENDPOINTS

4.1 Baseline Definition

As a rule, baseline values are defined as the last available value prior to the first injection of E6011 for all longitudinal endpoints unless explicitly stated otherwise in this document. As defined per protocol all assessments are performed before the IMP administration.

Change from baseline values are defined as:

Value measured after first dosing – Baseline value

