- 2) Rescue Period (Open label): comprises from week 12 to week 24 for non-responders. Subjects with a reduction in the CDAI of less than 70 compared to baseline after finishing evaluation in Week 12 of the remission-induction period are to move on to the rescue period. The rescue period is to last 12 weeks, with 10 mg/kg of E6011 administered in an unblinded manner on Week 12, Week 13, Week 14 and every two subsequent weeks until Week 22.
- 3) Extension Period (Open label): comprises from week 12 to week 52 for responders at week 12 and from week 24 to week 64 for non-responders at week 12. Subjects who

finished evaluation at Week 12 of the remission-induction period and had a CDAI response of 70 or more, and subjects who moved on to the rescue period and finished evaluation at Week 24 with a CDAI response of 70 or more are to move on to their respective extension period. The extension period is to last 40 weeks, with 10 mg/kg E6011 administered in an unblinded manner every four weeks up to Week 48(responders) or Week 60(non-responders).

- 4) Post-Observation Period: After the extension period of the clinical trial has been finished or discontinued, examinations are to be carried out 28 days after the completion or discontinuation of the extension period and 70 days after the last administration of the IMP.
- 5) Follow-up Period: PML onset is to be investigated over the phone, etc. every 6 months in the two-year follow-up period after the last IMP administration.

Four analysis periods are defined:

- 1) Remission-induction period: as defined above.
- 2) Rescue period: as defined above. This period will be used only for adverse events endpoints.
- 3) Entire administration period comprises the remission-induction period, the rescue period, the extension period and the post-observation period as defined above.
- 4) Follow-up period: as defined above.

Analyses of the remission-induction period will be performed after the remission-induction period is completed. Analyses of the entire administration period (remission-induction period, rescue period, extension period and post-observation period) will be performed after the post-observation period is completed. Analysis of the follow-up period will be performed after the follow-up period is completed.

In all TFLs that are displayed by treatment groups they will refer to the remission-induction treatments.

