6.8 Efficacy Analysis

Efficacy analysis will be based in the FAS and PPS populations. Primary analysis will be produced in the FAS population. Primary analysis will be repeated in the PPS population as a sensitivity analysis.

Efficacy analysis will be done for the remission-induction period and the entire administration period.

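### The SAP never summarises efficacy in rescue entrants on their own: neither their Week 12 to 24 change on E6011 nor the number meeting the Week 24 transition criterion is tabulated

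*SAP*

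**What the plan says.** Rescue repeats the induction schedule, open-label, in patients whose CDAI fell by less than 70 at Week 12 (protocol 9.1.3, 9.4.1). For those randomised to placebo it is their first course of E6011. Protocol 9.1.3 sends on to the extension "Subjects with a reduction in the CDAI of 70 or more compared to baseline or Week 12 at evaluation in Week 24"; those who miss the threshold on both references are discontinued. SAP 3.2 repeats the rule.

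On analysis, SAP 6.1 lists four periods:

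- The rescue entry reads "Rescue period: as defined above. This period will be used only for adverse events endpoints".
- The next entry reads "Entire administration period comprises the remission-induction period, the rescue period, the extension period and the post-observation period as defined above".

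SAP 6.8 then states: "Efficacy analysis will be done for the remission-induction period and the entire administration period". Protocol 9.7.1.10 agrees: "The same efficacy, pharmacokinetic, biomarker, immunogenicity, and safety analyses performed for the remission-induction period are to be performed". SAP 6.1 also says that treatment groups in all outputs are the induction-period treatments. SAP 6.8.2 names no visit after Week 12.

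Response has one reference. In protocol 9.5.1.3.1, "CR70 and CR100 are defined as clinical response with a decrease of" at least 70 or 100 points from baseline. The documents differ on what baseline is:

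- Protocol 9.3.1: "Patients with a baseline (at Week 0 before the start of IMP administration) disease severity ranging from moderate to severe".
- SAP 4.1: "baseline values are defined as the last available value prior to the first injection of E6011 for all longitudinal endpoints".

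**The concern.** A placebo non-responder's change from Week 0 to Week 24 is the sum of 12 weeks on placebo and 12 weeks on E6011. A table anchored only at Week 0 cannot separate the two parts. A table by randomised arm also mixes these patients with Week 12 responders, who are on a different dosing interval at the same visits.

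The rule that decides who continues accepts either of two references, while the efficacy tables use one. A reader of the report could not see how many rescue entrants qualified, or on which reference. Long-term efficacy is a stated secondary objective. With enrolment closed at 25 (protocol 9.7.2), the crossed-over placebo patients are a sizeable share of everyone given an induction course of E6011.

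**Working it through.** **The plan's own figure.** The documents give none for rescue. Their one operating characteristic is a probability above 80% of confirming efficacy with 20 per group and a true difference of 40%. By exact enumeration with Jeffreys priors it comes to 80.7% to 84.9% for placebo rates of 5% to 50%. It reproduces, and the rescue point does not touch it.

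**Which patients share a table row.** By the protocol's Table 4, CDAI and PRO2 are recorded in rescue at Weeks 14, 16, 20 and 24, and in responders at Weeks 16, 20 and 24. Only Week 14 holds rescue patients alone. Colonoscopy is not scheduled in rescue, so SES-CD does not arise.

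**Decomposition.** Change (0 to 24) = change (0 to 12) + change (12 to 24). Two illustrative placebo patients, both rescue entrants:

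| | Week 0 | Week 12 | Week 24 | Fall from Week 0 | Fall from Week 12 | CR70 from Week 0 | Transition criterion |
|---|---|---|---|---|---|---|---|
| A | 300 | 330 | 255 | 45 | 75 | no | met, through Week 12 |
| B | 300 | 240 | 225 | 75 | 15 | yes | met, through baseline |

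Patient A continues but is a CR70 non-responder against Week 0. Patient B is a CR70 responder although 60 of the 75 points fell on placebo.

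**How often the references disagree.** The documents give no CDAI means or SDs, so every input here is an assumption: normal 12-week changes, SD 60, 80 or 100, mean placebo fall 30 or 60, mean rescue fall 0, 40 or 80, the two changes independent (18 scenarios, simulated).

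- Share entering rescue = Φ((70 − mean placebo fall)/SD). Lowest: Φ((70 − 60)/100) = 54%. Highest: Φ((70 − 30)/60) = 75%. With an average arm of 25/2 = 12.5 that is 6.8 to 9.4 patients, about 7 to 9.
- CR70 from Week 0 and from Week 12 disagree in about 12% to 21% of entrants, or one or two patients.
- The net difference (Week 0 rate minus Week 12 rate) runs from about −8 to +14 percentage points.
- The Week 0 CR70 rate lies 2 to 14 points below the share meeting the either-reference criterion.

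A second set of assumptions (placebo fall 20 to 60, rescue fall 40 to 70, SD 70 to 90, slope of rescue change on placebo change 0 or −0.3) gave 16% to 22% disagreement and a net difference of about −9 to +8 points.

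**Sensitivity with no drug effect in rescue** (mean placebo fall 60). The Week 12 rate is 1 − Φ(70/SD).

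| SD | CR70 from Week 0 | CR70 from Week 12 |
|---|---|---|
| 60 | 24% | 12% |
| 80 | 24% | 19% |
| 100 | 24% | 24% |

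**Regression to the mean.** Take SD 60, mean placebo fall 60, no drug effect, and a correlation of −0.5 between the two changes. Entrants are those below z = (70 − 60)/60 = 0.167, whose mean z is −φ(0.167)/Φ(0.167) = −0.393/0.566 = −0.695. Their expected fall in rescue is −0.5 × 60 × (−0.695) = 21 points, and about 19% show CR70 from Week 12.

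**Precision.** The exact 95% interval is 12% to 74% for 4 of 10, and 4% to 78% for 2 of 6.

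**The case against.** The strongest reply is that the plan does what the protocol asks, and that more tables would add little. Its parts fare differently.

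- *Rescue is not shut out of efficacy.* Correct. A reader might infer from the adverse-events sentence that it is, but the entire administration period includes rescue and SAP 6.8 analyses efficacy on it. The restriction applies to rescue as a stand-alone period.
- *The SAP does not contradict a success rule.* Correct. The Week 24 rule governs transition and discontinuation, is not a listed endpoint, and is restated in the SAP. Scoring response from baseline follows the protocol's definitions. Patient B is no false success under the rule, since baseline is an accepted reference. What remains is that the rule's result is not reported.
- *Disposition already counts failures.* Partly. SAP 6.3 has a discontinuation reason covering a CDAI fall below 70 after rescue, but it is merged with other lack of effect and does not say which reference was met by those who continued.
- *Scoring only against Week 0 is not certain.* Correct. Read literally, SAP 4.1 gives placebo patients a Week 12 baseline, and patient A would then be a responder. That reading makes the placebo change to Week 12 zero by construction and breaks the primary endpoint, so Week 0 is the workable reading. Either way each patient has one reference and the criterion needs two.
- *Week 12 anchoring has its own bias.* Correct, as the 21-point example shows. It limits what the tables can claim but is no reason to pool these patients with maintenance patients.
- *The analysis is exploratory and rescue mainly offers access to E6011.* True. This keeps the request to descriptive tables.

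**Conclusion.** The gap stands. Followed as written, the plan isolates neither the Week 12 to 24 change in rescue entrants nor the number meeting the Week 24 criterion, and its Week 16, 20 and 24 rows combine two dosing schedules. These findings rest on the text alone.

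The numerical size is modest and rests wholly on assumed CDAI distributions: about one or two of 7 to 9 placebo rescue entrants classified differently. Because the sign of the net difference changes across plausible inputs, it would be wrong to conclude that Week 0 scoring systematically flatters or penalises E6011. The 24% against 12% contrast appears at the smallest SD and the larger placebo fall, and is gone at SD 100.

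It would also be wrong to expect the added tables to yield an E6011 induction effect. They would be uncontrolled, open-label, very imprecise and subject to regression to the mean. The primary analysis is not affected by the rescue point. The SAP 4.1 wording is a separate defect that does bear on it, and needs settling before any change from baseline is computed.

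**What to change.** Amend SAP 6.1 and 6.8 to add descriptive tables for rescue entrants, separately for prior placebo and prior E6011:

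1. CDAI and PRO2 change, and CDAI CR70 and CR100, at Weeks 14, 16, 20 and 24, each against both Week 0 and Week 12.
2. The number meeting the Week 24 criterion as the protocol states it, with all rescue entrants as denominator.

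In the same amendment, reconcile SAP 4.1 with the protocol's Week 0 baseline, for instance by tying baseline to the first administration of IMP (either arm), and name Week 12 as a second reference for the rescue tables only.

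Label the tables descriptive, state that Week 12-anchored change includes regression to the mean, and say that they are not an estimate of drug effect.

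The cost is SAP wording and a few tables from data already scheduled. No visit, treatment rule or primary analysis changes. Protocol 9.7 has the analysis plan fixed before each period's database lock, so this belongs in the version governing the entire administration period. The baseline wording should be settled before the remission-induction lock.

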E6011	10 mg/kg	Aqueous solution	10 mg/kg of E6011 dosing solution (approximately 100 mL) is to be infused intravenously over the period of approximately 30 minutes.	Remission-induction period: 12 weeks Rescue period: 12 weeks Extension period: 40 weeks
Placebo	N/A	Aqueous solution	The physiological saline solution (approximately 100 mL) is to be infused intravenously over the period of approximately 30	Remission-induction period: 12 weeks Rescue period: No administration

Date: 18-Apr-2022 version 11.0 Confidential Page 34 of 80

!	minutes.	Extension period: No
		administration

N/A: Not applicable

The Principal Investigator shall appoint the Clinical Trial Centre's pharmacist or a person with appropriate qualifications as the unblinded trial staff (unblinded trial pharmacist, unblinded trial doctor, or unblinded trial coordinator). Until maintaining the blinding is no longer necessary, such as at code break, only the unblinded trial pharmacist or unblinded trial doctor can prepare the IMP. The unblinded trial pharmacist or unblinded trial doctor, upon confirming the subject's allocation group and the subject's weight, is to prepare an E6011 dosing solution. The unblinded trial pharmacist or unblinded trial doctor is to create an IMP preparation record and deliver prepared IMP to the IMP administration trial staff, maintaining the blinding. Only an IMP administration trial staff who has undergone a proper training can administer the IMP. In the double-blind period, the unblinded trial pharmacist or unblinded trial doctor is to dispense the IMP after placing a semi-transparent or non-transparent concealing cover on the intravenous drip bottle sealed using a sticker, and after the IMP administration has been completed, the unblinded trial staff is to confirm that the seal sticker is still intact indicating that the concealing cover has not been taken off from the bottle until the end of administration, and that the blinding is thus maintained.

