# 9.7.2 Target sample size

The number of subjects in this clinical trial was determined considering stimulation-generated operating characteristics relating to efficacy assessment, based on efficacy outcomes of the 101 trial and of similar drugs. With 20 subjects allotted to each group, if the actual difference in CR100 response rate between the E6011 group and placebo group is 40% or more, the probability of confirming the efficacy of E6011 is above 80%.

The number of enrolled subjects was 25 at the end of the recruitment. Therefore, the sample size will be reduced to 25 subjects, but the analysis plan will remain unchanged and performed in accordance with section 9.7 Statistical method.

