3.3.2 Secondary objectives

- To examine the efficacy and safety of a long-term administration of E6011.
- To evaluate the pharmacokinetics and immunogenicity of E6011.

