5.2 Safety Population

Safety analysis set is a set of subjects to whom the IMP has been administered, and who had 1 or more evaluable, post-IMP administration safety data points. Safety endpoints include adverse events, laboratory values, vital signs, weight, physical examination, standard 12-lead ECG, neurological symptoms and blood CD4⁺ cell count. Patients in the safety population will be analyzed according to the treatment actually received at remission-induction period.

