Duration of IMP exposure is defined as date and time of last IMP administration – date and time of first double-blind IMP administration + 14 days, regardless of unplanned intermittent discontinuations.

Duration will be presented in days.

Duration of IMP exposure will be summarized descriptively as a quantitative variable (number, mean, SD, median, minimum, and maximum). In addition, duration of treatment exposure will also be summarized categorically by numbers and percentages for each of the following categories and

cumulatively according to these categories: ≤ 1 week, (1 week, 4 weeks], (4 weeks, 8 weeks], (8 weeks, 12 weeks], (12 weeks, 22 weeks], (22 weeks, 48 weeks], (48 weeks, 60 weeks], >60 weeks.

Compliance:

A given administration will be considered non-compliant if the patient did not take the planned dose of treatment as required by the protocol. No imputation will be made for patients with missing or incomplete data. The percentage of noncompliant administrations will be descriptively summarized by treatment. Percentage of noncompliant administrations is defined as number of non-compliant administrations divided by the number of total administrations.

Treatment compliance (%) by period is defined as the actual number of IMP administration divided to the planned number of administrations.

Treatment compliance will be summarized by descriptive statistics for the FAS populations by treatment and study period. In addition, the percentage of patients per compliance level will be also summarized: $\leq 60\%$, (60%, 80%], (80%, 100%].

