6.9.1 Adverse Events

Treatment-emergent adverse events are adverse events that developed or worsened during the treatment-emergent adverse event period (from first date of IMP until last date of IMP +70 days).

The primary focus of adverse event reporting will be on treatment-emergent adverse events. Post-treatment PML events will be described in a separate table, as well as pre-treatment, treatment emergent and post-treatment deaths.

Adverse events will be considered only in the period in which it starts.

The following summaries will be generated for the safety population.

- a. Overview of adverse events during all study and by analysis period, summarizing number (%) of patients with any
 - Adverse event
 - Treatment-emergent adverse event
 - Serious treatment-emergent adverse event
 - Non-serious treatment-emergent adverse event
 - Treatment-emergent adverse event leading to death
 - Treatment-emergent adverse event leading to permanent treatment discontinuation
 - Treatment-emergent adverse event related to study drug
- b. All adverse events during all study by primary SOC and PT, showing number (n) and percentage (%) of patients with at least 1 adverse event sorted by the SOC internationally agreed order. The other level (PT) will be presented in alphabetical order
- c. All treatment-emergent adverse events by analysis period and by primary SOC and PT, showing number (n) and percentage (%) of patients with at least 1 treatment-emergent adverse event sorted by the SOC internationally agreed order. The other level (PT) will be presented in alphabetical order

- d. All treatment-emergent adverse events related to IMP by analysis period and by primary SOC and PT, showing the number (n) and percentage (%) of patients with at least 1 treatment-emergent adverse event, sorted by the internationally agreed SOC order. The other level (PT) will be presented in alphabetical order
- e. All treatment-emergent adverse events by analysis period and by maximal severity, presented by primary SOC and PT, showing the number (n) and percentage (%) of patients with at least 1 treatment-emergent adverse event by severity (i.e., mild, moderate, or severe), sorted by the sorting order defined above.
- f. All treatment-emergent serious adverse events by analysis period and by primary SOC and PT, showing the number (n) and percentage (%) of patients with at least 1 serious treatment-emergent adverse event, sorted by the internationally agreed SOC order.

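### SAP 6.9.4 stops ECG and neurological summaries at Week 12, against the protocol and SAP 6.9; separately, no AE or exposure summary covers all E6011-treated patients from their first E6011 dose

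*SAP*

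**What the plan says.** **ECG and neurological data.** SAP 6.9.4 describes a single by-arm summary, the percentage of patients with an abnormal finding, and limits it to the first 12 weeks. Protocol 9.7.1.8.5 (ECG) and 9.7.1.8.7 (neurological symptoms) ask for normal and abnormal counts in shift tables. Protocol 9.7.1.10 then repeats the induction-period safety analyses for the whole dosing period. Within the SAP, 6.9 opens by saying that safety evaluations in the four analysis periods will be analysed, 6.9.3 covers vital signs in three of them, and the synopsis keeps shift tables for ECG and neurological symptoms. SAP 6.11 declares no change from the protocol's statistical section.

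**Grouping.** SAP 6.1: "In all TFLs that are displayed by treatment groups they will refer to the remission-induction treatments". SAP 5.2: "Patients in the safety population will be analyzed according to the treatment actually received at remission-induction period". The placebo row of Protocol Table 1 (9.4.1) reads "Rescue period: No administration", and says the same for the extension, so every patient dosed from Week 12 onwards receives E6011.

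**Periods and clocks.** SAP 6.1 defines four analysis periods: induction, rescue (AEs only), entire administration, and follow-up. The extension has none of its own. On AEs, SAP 6.9.1 says: "Adverse events will be considered only in the period in which it starts". Treatment-emergent AEs are counted from the first IMP dose. Exposure in SAP 6.7 is the last administration minus the "date and time of first double-blind IMP administration + 14 days, regardless of unplanned intermittent discontinuations". Protocol 9.5.1.5.1 defines IMP to include placebo.

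**Objective and size.** A secondary objective (SAP 3.3.2) is: "To examine the efficacy and safety of a long-term administration of E6011". Protocol 9.7.2 states: "The number of enrolled subjects was 25 at the end of the recruitment".

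**The concern.** Two things are at stake, and they differ in weight.

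The first is a contradiction. Protocol 9.5.3 requires regular neurological assessment throughout the trial because a PML risk cannot be excluded. The one SAP section that specifies the neurological and ECG output stops where long-term E6011 treatment begins. For a placebo-arm patient the 12-week window contains no E6011 exposure at all, because the Week 12 assessments precede the Week 12 dose. For an E6011-arm patient it covers 12 of up to 64 weeks. A programmer who follows 6.9.4 would produce no systematic normal/abnormal summary for the rest.

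The second is an omission. Long-term E6011 safety is an objective in a trial of 25 patients, yet every column is the induction arm. With 1:1 allocation, the E6011 column holds roughly half of those enrolled, while most or all of the placebo arm may later receive E6011. After Week 12 the placebo column is an E6011 column under another name, and nothing counts from the first E6011 dose across everyone who had one.

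**Working it through.** The plan states no figure on this point, so there is none to reproduce. The check compares the texts and then applies the plan's own schedule.

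**Step 1: ECG and neurological output side by side.**

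| Source | Output | Time covered |
|---|---|---|
| Protocol 9.7.1.8.5, 9.7.1.8.7 with 9.7.1.10 | Shift table | Induction, then entire dosing period |
| SAP synopsis, Safety | Shift table | Not stated |
| SAP 6.9 | Safety evaluations in general | Four analysis periods |
| SAP 6.9.4 | Percentage with an abnormal finding | First 12 weeks |

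SAP 6.9.4 differs from the protocol on both output type and period, from SAP 6.9 on period, and from the synopsis on output type only.

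**Step 2: scheduled assessments after the cut-off.** Input: the ECG and neurological rows of Protocol Table 4, excluding baseline and unscheduled discontinuation visits. The Week 12 visit is counted as inside the window.

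| Pathway | Post-baseline visits | After Week 12 |
|---|---|---|
| Week 12 responder, completes | 12, 24, 36, 52 | 3 of 4 (75%) |
| Week 12 non-responder, completes | 12, 24, 36, 48, 64 | 4 of 5 (80%) |
| Stopped at Week 24 | 12, 24 | 1 of 2 (50%) |

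**Step 3: what starts at the first E6011 dose.**
- E6011 arm: first IMP is first E6011, so its AE and exposure tables already start there.
- Placebo-arm non-responders: the rescue AE tables start there, but cover Weeks 12 to 24 only.
- Placebo-arm Week 12 responders: nothing starts there.
- Placebo-arm non-responders after Week 24: their events appear only in the entire administration period, which also contains their placebo time.
- All exposed patients pooled: no such table. SAP section 10 lays tables out by treatment group and race, where the level for all patients refers to race.

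**Step 4: exposure for placebo-arm patients with full scheduled dosing.** Last doses fall at Week 48, 60 or 22 (Protocol 9.4.1), and first E6011 at Week 12.
- SAP formula: last dose week × 7 + 14 days.
- From first E6011: (last dose week − 12) × 7 + 14 days.

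| Pathway | SAP formula | From first E6011 | Difference |
|---|---|---|---|
| Responder | 48 × 7 + 14 = 350 | 36 × 7 + 14 = 266 | 84 (24% of 350) |
| Non-responder, completes extension | 60 × 7 + 14 = 434 | 48 × 7 + 14 = 350 | 84 (19% of 434) |
| Stopped after rescue | 22 × 7 + 14 = 168 | 10 × 7 + 14 = 84 | 84 (50% of 168) |

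**The case against.** **General lines in the SAP may already cover later visits.** SAP 6.1 summarises categorical variables at every scheduled visit, and 6.9 names all four periods. That is a fair reading of intent. But 6.9.4 is the specific section and it states a limit, which a general sentence does not override. The wording has to be reconciled.

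**Surveillance is not lost.** This stands. Protocol 9.5.1.5.7 has neurological abnormalities after dosing recorded as AEs and confirmed PML as an SAE, and 9.5.1.5.6 does the same for ECG abnormalities that meet the AE definition. A reader might infer that such events would disappear from the report; the documents do not support that. What is missing is the systematic shift summary.

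**Display by original arm is conventional and the analysis is descriptive.** This also stands. By-arm tables are not an error, the documents promise no pooled E6011 table, and exposure is labelled as IMP, so it is not mislabelled. Assigning AEs to their period of onset keeps the induction and rescue AE tables clean. Compliance is also separated: "Treatment compliance will be summarized by descriptive statistics for the FAS populations by treatment and study period". Protocol 9.7.1.8 groups safety by actual treatment without the restriction to induction in SAP 5.2. However, Protocol 9.7.1 says those sections mainly describe the induction period, so a clear departure cannot be claimed. The PML table is by treatment group in Protocol 9.7.1.11 too, so its layout is not a SAP deviation.

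**Protocol version.** The SAP cites protocol v10 and the supplied protocol is v11.0, so the v10 wording behind the statement in SAP 6.11 cannot be checked. The conflict of 6.9.4 with SAP 6.9 and the synopsis does not depend on it.

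**Conclusion.** The point holds in two parts.

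**Wrong as written:** SAP 6.9.4 contradicts the protocol's shift tables, their repetition for the entire dosing period, and SAP 6.9. If followed, half to four fifths of scheduled post-baseline ECG and neurological assessments go unsummarised, depending on pathway. This rests only on the documents' schedule and on counting Week 12 as inside the window.

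**A cheap improvement:** the long-term safety objective has no AE or exposure summary covering all E6011-exposed patients from first E6011 dose. The 84-day difference assumes full scheduled dosing. The documents give no arm sizes for the 25 enrolled and no crossover count, so the gain in denominator cannot be fixed beyond a ceiling of 25.

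Two stronger readings should be avoided. A reader might infer that the synopsis contradicts the 12-week limit, but it gives no time window and conflicts only on output type. A reader might also infer that no AE table starts at the first E6011 dose, but the E6011-arm tables do, and so do the rescue tables for placebo-arm non-responders over Weeks 12 to 24.

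Neither part touches the primary analysis. Both should be changed.

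**What to change.** 1. Replace SAP 6.9.4 with normal/abnormal shift tables for ECG and neurological symptoms at all scheduled visits, for both the remission-induction and the entire administration periods. If a narrower output is intended, record it as a modification in SAP 6.11.
2. Keep the by-arm tables and label the placebo column placebo/E6011 where it covers time after Week 12.
3. Add an AE and exposure summary counted from the first E6011 dose, with columns E6011-E6011, placebo-E6011 and total. State that it is descriptive and not a randomised comparison.
4. Add a total column to the PML follow-up table.

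The cost is SAP wording and a few tables from data already collected. Protocol 9.7 fixes the plan before each database lock, so the long-term tables can be settled before the entire administration lock. The downside is small columns with 25 patients.
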